10. DATA ANALYSIS

Data Quality Assurance

The PI will be solely responsible for the accuracy of the data. Single data entry will be performed with plans to check 10% of primary variables as a quality control. Single data entry error rates are slightly higher than 0.5% when performed by trained staff and the minimally improved error rate through double data entry is outweighed by substantial cost savings for single data entry. Data anomalies will be reviewed by the PI and clarification and/or correction will be performed. Incomplete entries will be reviewed and corrected if information is available.

Data Entry and Storage

Data will be entered in redcap database accessed through desktop computer of the PI located in a locked office in TIRR Memorial Hermann and Craig Hospital. Any paper documents will be filed in a study binder in a locked drawer in the office of the PI with HIPPA information removed. 5 years after manuscript publication, the paper reports will be placed into the shredder bins for destruction.

11. SAMPLE SIZE AND STATISTICAL METHODS

Determination of Sample Size:

The purpose of the proposed pilot trial is to test the feasibility of conducting a randomized control trial comparing high vs. low Vt MV. Given the complexity of this study and practice variation, it is essential to evaluate recruitment and study procedures. Our cohort study data suggest that approximately 19 patients per year will meet eligibility. Based on Fenton et al. study comparing high vs. low Vt MV in SCI, we anticipate a total recruitment rate of 80% (i.e., that 80% of the eligible would consent for the study), i.e., on average, we are expecting to enroll at least 10-12 participants with SCI who are on mechanical ventilation per year for mechanical ventilation group and total of 30 subjects for 3 years.

For the control group, we will recruit cervical SCI (neurological level C1-C5) who are not dependent on mechanical ventilation at admission to our acute inpatients rehabilitation facility. We plan to recruit a total of 15 subjects in 2 years. This is a pilot study based on feasibility of completing study within the above time frame this sample size was determined. We will have atleast 15 subjects in each group for the analysis.

Statistical and Analytical Plans:

Baseline data and unadjusted analysis of outcome variables will be presented as mean with standard deviation (SD) for a continuous variable with normal distribution otherwise as median with interquartile range (IQR). Categorical and ordinal data will be reported as totals and frequencies for baseline data and unadjusted analysis of outcome variables.

Aim 1: Respiratory outcomes: We will report relative risk with credible interval and posterior probability. We will use neutral prior, and for binary outcomes, this will be centered at RR of 1 with 95% credible interval of 0.3 to 3. Bayesian inference combines a prior or an estimated effect distribution based on previous studies and likelihood, which summarizes findings from the present study.³⁵ All Bayesian analyses will use similar models as the frequentist analyses. We will report risk ratios with 95% credible intervals and posterior probability of benefit or harm associated with the intervention.

Aim 2: The number of patients contacted and recruited per month will be presented, and we will use the CONSORT diagram to summarize the numbers and reasons related to recruitment, follow-up, and dropout. The main feasibility outcomes include recruitment rate, adherence rate, and retention rate.

We will summarize these outcomes by arm using frequency and percentage. We will inspect these percentages relative to our feasibility targets.

Aim 3: Individual inflammatory marker levels will be presented as mean with standard deviation. A linear mixed model will be constructed on cytokine levels, adding time and randomization group as factors in the model. In this model, the interaction between time and group will be used to study differences over time between groups. A random intercept for the patient will be included to account for within-patient correlation. If the residuals are not normally distributed in linear mixed model analyses, the data will be transformed (e.g., natural logarithm), or an alternative distribution will be used. The relation between cytokine levels and the development of pneumonia or pulmonary adverse events will be studied with a multivariate logistic regression analysis. A risk ratio with 95% confidence interval (95% CI) will be presented

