3. STUDY POPULATION

Sample Size: We plan to recruit 45 subjects (15 in low Vt, 15 in high Vt, and 15 in the control group). We will recruit 30 adults with acute cervical SCI admitted on mechanical ventilation from TIRR MHH and Craig Hospital and an additional 15 people with acute cervical SCI not dependent on mechanical ventilation at admission to serve as controls from TIRR MHH.

Criteria for Recruitment: All consecutive patients with SCI admitted to TIRR MHH and Craig Hospital will be screened for eligibility based on inclusion and exclusion criteria during the study period. The screening will involve the review of history from the patient or primary admitting clinician. If a patient meets eligibility criteria, the research coordinator will provide further information on the study, answer any questions, and recruit if they are willing to participate and provide consent.

Inclusion Criteria: Subjects must meet all of the inclusion criteria listed below to participate in this study.

- Adult patients \geq 18 years (Lung volumes and ventilator settings are different for ages <18 years).
- Acute SCI of duration \leq four months
- Mechanical ventilation subjects: traumatic or non-traumatic cervical SCI with neurological level C1-C5 admitted to our acute inpatient rehabilitation facility (AIR) on mechanical ventilation.
- Control subjects: traumatic cervical SCI admitted to our acute inpatient rehabilitation facility (AIR) who are not dependent on mechanical ventilation.

Exclusion Criteria: All subjects meeting any of the exclusion criteria listed below at baseline will be excluded from participation.

- Severe dysphagia due to concomitant brain stem injury, which increases the risk of pneumonia
- Severe brain injury resulting in dysphagia and inability to follow instructions to perform vital capacity measurements
- ARDS or severe lung disease (required supplemental oxygen or ventilator prior to SCI) at the time of admission (these conditions will not allow patients to randomize because target Vt may below)
- Prolonged antibiotics for > 3 weeks at the time of admission due to infection (e.g., osteomyelitis, epidural abscess, etc.),
- Presence of diaphragmatic pacemaker.

Withdrawal Criteria: Possible reasons for discontinuation of study intervention: Intolerance to proposed ventilator settings.

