Subject Replacement: Subjects who drop out will be replaced by screening the inpatient unit. Subjects that drop out will be followed for secondary outcomes collected via the EMR while they remain at TIRR.

4. TRIAL SCHEDULE:

Participants will be enrolled in the study upon consent within 48-72 hrs of admission to TIRR MHH or Craig Hospital, and participation will end on discharge from respective hospital. The trial will start upon IRB and respective hospital approval on July 1, 2021, and end on June 30, 2024.

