8. TREATMENT

The current clinical practice guidelines recommend a higher tidal volume starting at 15 ml.kg predicted body weight (pbw) and up to 25 ml/kg pbw. These guidelines were written based on a small retrospective study and biological plausibility. People with SCI suffer hypoventilation due to paralysis of the muscle of inspiration. However, current data in people with and without ARDs suggests that lower tidal volume lowers the risk of morbidity and mortality and improves respiratory outcomes. Cohort study performed at TIRR also suggests that lower tidal volumes may lower the risk of pneumonia.

Our cohort study and a recent survey of physicians managing mechanical ventilators for people with SCI suggest practice variation in ventilator settings used for people with SCI.

Data from our center and international survey:

Variation in ventilator settings used for patients with acute SCI in acute care hospital at the time of discharge to a rehabilitation facility (Unpublished data): We collected data on 91 patients who required mechanical ventilation at the time of admission to acute inpatient rehabilitation (AIR) facility from 2015-2019. We noted variation (Figure 1.) in ventilator modes and settings used at acute care hospitals at the time of discharge. Median (interquartile range) tidal volumes were 7.5 (6.7-8.5) ml/kg pbw on admission to AIR facility or at the time of transfer from acute care hospital. 84% of patients were receiving PEEP on admission. After admission to the AIR facility, all patients were weaned off PEEP within the next 1-2 days and switched to assist control mode. Patients' tidal volumes were gradually increased to prevent atelectasis per SCI clinical practice guidelines.⁴ As a result, the median (IQR) tidal volumes received in rehabilitation hospital were 14 (13-16) ml/kg pbw. Our data suggest that ventilator settings used in acute care hospital and rehabilitation vary.

[figure not shown]

Figure 1: Ventilator modes at the time of discharge from acute care hospital

Abbreviations: Assist control; **SIMV:** Synchronized intermittent mandatory ventilation; **PS:** pressure support; **CPAP:** Continuous positive airway

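### Replaced dropouts are not clearly followed for pneumonia, the primary outcome, at both hospitals; as a minor clarification, the yearly enrolment figure lacks its derivation

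*Combined protocol and SAP*

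**What the plan says.** **Numbers and sites.** Section 3 (Sample Size) states: "We plan to recruit 45 subjects (15 in low Vt, 15 in high Vt, and 15 in the control group". Two hospitals supply the ventilated patients: "We will recruit 30 adults with acute cervical SCI admitted on mechanical ventilation from TIRR MHH and Craig Hospital".

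**Dropouts.** Section 3 (Subject Replacement) states: "Subjects who drop out will be replaced by screening the inpatient unit". The next sentence provides for following dropouts through the electronic record, for secondary outcomes, during their stay at TIRR. It mentions neither the primary outcome nor Craig Hospital.

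**Outcomes.** Section 6 (Outcomes) makes pneumonia episodes primary and the feasibility measures secondary. It anticipates 80% retention and 80% adherence among those enrolled.

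**Analysis numbers.** Section 11 says: "We will have atleast 15 subjects in each group for the analysis". It does not say whether the 15 is counted before or after replacement.

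**Accrual.** Section 11 starts from this: "Our cohort study data suggest that approximately 19 patients per year will meet eligibility". It assumes that 80% of eligible people consent, and then concludes: "on average, we are expecting to enroll at least 10-12 participants with SCI who are on mechanical ventilation per year", with 30 over three years. For controls it says: "We plan to recruit a total of 15 subjects in 2 years".

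**The concern.** A randomised comparison is protected by keeping everyone who was randomised and knowing their primary outcome. Dropping out may be related both to the assigned tidal volume and to respiratory trouble. If dropouts are replaced and their pneumonia is not recorded, the arms compared are no longer the arms randomised, and the bias could run in either direction. With 15 per arm, one patient whose pneumonia goes unrecorded shifts that arm's observed risk by 1/15, or 6.7 percentage points. The stopping check at 50% recruitment in Section 9 also uses pneumonia risk.

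The accrual sentence is a lesser matter. Section 11 bases the sample size on what can be completed in the time frame and gives no power calculation. The yearly rate is therefore part of the stated basis for the design, and a reader cannot reproduce it.

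**Working it through.** **1. Does any section secure pneumonia data for replaced dropouts?**

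| Section | What it provides | Does it settle the matter for replaced dropouts? |
|---|---|---|
| 3, Subject Replacement | Replacement; follow-up for secondary outcomes at TIRR | It is the only text on dropout follow-up, and it is narrower than needed |
| 6, Study procedures | Adverse events and outcome data from day 0 to discharge | Does not mention dropouts; its record-extraction sentence names only TIRR |
| 7 | Clinical outcomes taken from the records of each hospital | Covers both sites; does not mention dropouts |
| 8, Blinding | A panel determines the primary outcome | No exclusion of dropouts, but no commitment to include them |
| 9, Adverse events | Pneumonia counts as an adverse event; recording runs to study completion | Does not say that the panel judges these events for dropouts |
| 9, Safety Monitoring Plan | No patient removed; data kept for intention to treat | Written about changes of ventilator settings after desaturation |

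The general provisions point towards full follow-up. The specific rule for dropouts points the other way.

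**2. Illustration of size**

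- Inputs: 30 ventilated patients (Section 3) and 80% retention (Section 6).
- Assumption: every non-completer is a dropout who is replaced, and replacements are retained at the same 80%.
- Randomised: N × 0.80 = 30, so N = 30/0.80 = 37.5.
- Non-completers: 37.5 − 30 = 7.5.

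This is neither a forecast nor a bound. A patient who misses a sample may still have pneumonia recorded, which lowers the number with a missing primary outcome. Retention may also turn out below 80%, which raises it.

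**3. Accrual**

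Reproducing the plan's figure from its own inputs (19 eligible a year, 80% consent):

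- Per year: 19 × 0.80 = 15.2, against a stated 10 to 12 or more.
- Over three years: 15.2 × 3 = 45.6, against 30.
- Time to 30: 30/15.2 = 1.97 years, against 3.

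The stated figure is not reproduced. Three unstated steps might lie behind it:

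- *Retention, or retention and adherence, also applied:* 19 × 0.80² = 12.2 a year, or 19 × 0.80³ = 9.7. Both act after enrolment, whereas the figure is described as enrolment.
- *The 19 includes controls:* 45.6 is close to the planned 45. Removing 15 controls leaves 30.6, and 30.6/3 = 10.2 a year. The separate two-year control timeline weighs against this.
- *The 19 counts ventilated admissions before exclusions:* Section 8 says "We collected data on 91 patients who required mechanical ventilation at the time of admission to acute inpatient rehabilitation (AIR) facility from 2015-2019". That is 91/5 = 18.2 a year if the period is five full years, or 91/4 = 22.75 if it is four (the length is my assumption). The plan does not say that the 19 comes from these data.

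The plan states none of these steps. Nor does it say whether the 19 covers one hospital or both.

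**The case against.** **On dropouts.** The strongest reply is that the Section 3 sentence is merely loose. The secondary outcomes defined in Section 6 are feasibility measures, so a literal reading fits poorly with collection from the medical record. Other parts of Section 6 also name only TIRR, so the site wording need not be a limit specific to dropouts. The one listed reason for discontinuing the intervention is intolerance of the settings (Section 3). That is close to the case where Section 9 keeps the patient and applies intention to treat. What would remain is mainly withdrawal of consent (Section 12), where record review may not be permitted.

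Much of this stands. It makes full follow-up the likely intention, and it means the fix must be confined to dropouts who still permit record review. It does not remove the conflict: Section 3 provides for dropouts and replaces them, Section 9 says nobody is removed, and no text says which governs.

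A reader might infer that pneumonia will certainly be missing for dropouts. The documents do not support that, given Sections 6 to 9. Nor do they support treating 20% of 30, or 6 patients, as a ceiling, or 15 × 0.80 = 12 per group as the number completing. The 80% is only anticipated, and replacement raises the number randomised.

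**On accrual.** The figure is worded as a minimum, and 15.2 satisfies it. Thirty patients in three years is reachable at either rate. This objection stands in full and reduces the matter to a request for clarification. Three stronger readings should be resisted:

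- *That 30 of 57 eligible (53%) misses the 80% recruitment target.* Thirty is a planned total, so enrolment may stop once it is reached, and the recruitment rate is defined as consenters over eligible people.
- *That replacement breaks the timetable, since 37.5 patients at 10 to 12 a year takes 3.1 to 3.75 years.* This combines a minimum rate with the assumption that every non-completer is replaced.
- *That the plan should simply say about 15 a year.* That figure would rest on a 19 whose scope is unknown.

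**Conclusion.** The dropout point holds and should be corrected. As worded, Section 3 replaces dropouts and limits their follow-up to secondary outcomes at one of two recruiting hospitals. Sections 6, 7, 8 and 9 lean the other way, but none clearly covers replaced dropouts. The exposure is a possible loss of the primary outcome for some randomised patients, with others substituted. The illustration of 37.5 randomised and 7.5 non-completers rests on the anticipated 80% retention and on replacement of every non-completer.

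The accrual point is a minor clarification: an unexplained, conservative floor of 10 to 12 against a computed 15.2 a year. It does not put the target of 30 in doubt.

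**What to change.** 1. Amend Section 3 (Subject Replacement) so that, for dropouts who still permit record review, pneumonia is collected from the medical record to discharge at both hospitals and judged by the panel described in Section 8.
2. State in Section 11 that every randomised patient, including replaced dropouts, stays in the intention-to-treat primary analysis and in the adherence and retention denominators. Reconcile this with the wording on withdrawal in Section 3 and on non-removal in Section 9.
3. Say whether 15 per group is before or after replacement. If replaced dropouts stay in the analysis, the number randomised to the two ventilated arms can exceed 30.
4. In Section 11, show the step that leads from 19 eligible and 80% consent to 10 to 12 a year. Say whether the 19 is ventilated patients only, whether it is before or after exclusions, and which hospital or hospitals it covers. Leave the stated rate unchanged until that is known.

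The cost is rewording and a little more record review. Section 7 already plans outcome collection from the records of both hospitals, and no patients are needed beyond the replacements already planned.

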2. HYPOTHESIS AND OBJECTIVES

We propose a pilot randomized comparative effectiveness trial comparing respiratory complications and inflammatory markers based on MV settings of 8-10 ml/kg pbw and higher Vt of 14-16 ml/kg pbw in people with acute cervical SCI in an acute inpatient rehabilitation hospital. Our **long-term goal** is to study optimal ventilator settings and treatment approaches in acute SCI to reduce infections and improve lifelong outcomes.

Objectives:

Objective 1: To compare MV outcomes of high vs. low Vt on the relative risk of pneumonia in the acute rehabilitation hospital.

Objective 2: To generate the feasibility data to inform the future RCT design. To achieve this objective, we will obtain the following data: a) Recruitment rate: the proportion of eligible people who provide consent (b) Adherence rate: the proportion of participants in each group who receive assigned intervention per protocol; (c) Retention rate: the proportion of participants in each group who complete all study procedures prior to discharge from our hospital; d) Missing data: Percentage of missing data in each group.

Objective 3: To analyze MV related lung injury inflammatory biomarkers in relation to tidal volume and outcomes.

Hypothesis:

Hypothesis 1: We hypothesize that Bayesian analysis will indicate a>70% probability of lower risk of pneumonia in people with acute cervical SCI receiving lower Vt MV than higher Vt.

Hypothesis 2: We hypothesize that we will be able to recruit **at least** 80% of eligible people each year and among recruited subjects, adherence and retention rate will be 80%, with less than 10% missing data on outcome measures.

Hypothesis 3.1: We hypothesize that MV-related lung injury inflammatory biomarkers (IL-1, IL6, IL-8, and tissue necrosis factor α levels) in serum and tracheal aspirate would be lower in the low Vt MV group compared to high Vt.

Hypothesis 3.2: People with acute cervical SCI receiving MV will have higher inflammatory markers levels than people with acute cervical SCI who do not require mechanical ventilation.

Hypothesis 3.3: People with acute cervical SCI independent of mechanical ventilation status who have higher inflammatory marker levels are more likely to develop pneumonia and other respiratory complications.

Potential Risks and Benefits:

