5. STUDY DESIGN

We propose a randomized comparative effectiveness trial to study systematically current Vt ranges to determine optimal settings to improve outcomes. Study participants will be randomly assigned to high tidal volume (14-16 ml/kg pbw) or low tidal volume of 8 to 10 ml/kg pbw within 48 hrs of admission. Subjects will be stratified based vital capacity at admission (≥ 5.8 cc/kg pbw) to ensure equal allocation of those with the most severe respiratory impairment and unlikely to wean from the vent. In our experience, vital capacity ≥ 5.8 cc/kg pbw was associated with higher odds of weaning. We will screen and recruit an additional 15 people with acute SCI not dependent on mechanical ventilation at admission to serve as controls. We anticipate 3 years to complete study recruitment. A 1:1 allocation ratio will be applied to the mechanical ventilation groups. Participants, principal investigator, outcome assessors, and statistician will be blinded to tidal volume assignment.

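### Aim 2 sets raw adherence and retention percentages from about 15 per arm against targets equal to the expected 80%, with no interval, so an observed shortfall is likely even if the trial runs as planned

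*Combined protocol and SAP*

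**What the plan says.** Section 11 gives the aim of the study: "The purpose of the proposed pilot trial is to test the feasibility of conducting a randomized control trial". Section 3 sets the group sizes, "15 in low Vt, 15 in high Vt, and 15 in the control group". Section 11 repeats them, "We will have atleast 15 subjects in each group for the analysis", and section 5 gives the allocation: "A 1:1 allocation ratio will be applied to the mechanical ventilation groups".

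The feasibility targets are in Hypothesis 2 (section 2). Besides recruiting at least 80% of eligible people, it expects that "adherence and retention rate will be 80%, with less than 10% missing data on outcome measures". The Outcomes text in section 6 gives the same 80% as the anticipated adherence and retention, so target and expected value coincide. Sections 2 and 6 define both rates as proportions within each group.

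The analysis in section 11, Aim 2, covers monthly numbers contacted and recruited, a CONSORT diagram with reasons for dropout, and then: "We will summarize these outcomes by arm using frequency and percentage". The comparison with the targets is the single sentence "We will inspect these percentages relative to our feasibility targets". Neither document section adds an interval, a tolerance, or a way of combining arms and measures.

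**The concern.** Aim 1 is reported with credible intervals and posterior probabilities, and the Aim 3 risk ratio with a 95% confidence interval. Aim 2, which serves the stated purpose, is the only aim with no statement of uncertainty.

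A target equal to the expected rate is close to the middle of the sampling distribution, so falling below it is common by construction. Fifteen participants per arm make the scatter wide. Without an interval, a reader of the final report cannot tell a shortfall due to chance from a real feasibility problem. Nor can the reader tell whether a result on target rules out a materially lower rate. The sponsor's decision about the full-scale trial depends on that distinction.

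**Working it through.** **The plan's own figure.** The documents give no precision or pass probability for the feasibility targets, so there is none to reproduce. The enrolment figures in section 11 (about 19 eligible a year, 80% consenting) give 19 × 0.80 = 15.2 a year and 45.6 over three years, against a stated floor of 10–12 a year and 30 in total. That is a separate matter. The calculation below uses only the group size and the 80% target.

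**Inputs.** n = 15 per ventilated arm (sections 3 and 11). Target 80% for adherence and for retention (sections 2 and 6), read generously as at least 80%, so 0.80 × 15 = 12 of 15. True rate set to the anticipated 80%. The documents give no correlation between adherence and retention, so I show a range.

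**One arm, one measure.** With X ~ Binomial(15, 0.8):

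P(X ≥ 12) = 0.2501 + 0.2309 + 0.1319 + 0.0352 = 0.648, so P(shortfall) = 1 − 0.648 = 0.352.

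**Four arm-level figures** (adherence and retention in two arms), independent:

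P(all four at or above 80%) = 0.648⁴ = 0.176, so P(at least one short) = 0.824.

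**Correlated adherence and retention.** An exact four-cell multinomial within each arm, with within-patient correlation φ:

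| φ | P(at least one of four short) |
|---|---|
| 0 | 82.4% |
| 0.25 | 79.0% |
| 0.50 | 75.0% |
| 0.75 | 69.5% |
| 1 (identical) | 58.0% |

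The last row is 1 − 0.648² = 0.580, because the four figures reduce to two.

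**Pooled over the two ventilated arms.** The target is 24 of 30. P(X ≥ 24 | n = 30, 0.8) = 0.607, so one measure falls short 39.3% of the time. At least one of two falls short 1 − 0.607² = 63.2% of the time under independence, and 39.3% if the two are identical.

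**Denominators other than 15.** Section 3 allows dropouts to be replaced, so arms may exceed 15. With 14, 16 or 17 per arm, the chance that at least one of four independent figures falls short is 96.0%, 87.2% and 90.9%. It exceeds 82.4% because 80% of those numbers is not whole and the count must be rounded up.

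**Precision of a result exactly on target** (Clopper–Pearson 95%): 12/15 gives 51.9% to 95.7%; 24/30 gives 61.4% to 92.3%.

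**Check on a possible remedy.** Requiring the whole 95% interval to lie above 80% would not work. At 28/30 the lower limit is 77.9%; at 29/30 it is 82.8%. So at least 29/30 is needed, with probability 30 × 0.8²⁹ × 0.2 + 0.8³⁰ = 0.0093 + 0.0012 = 0.0105 at a true 80%. Every count from 19/30 to 28/30 has an interval containing 80%.

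**The case against.** The strongest reply is that the plan contains no decision rule that could err. It says the percentages will be inspected. It does not say that each arm must reach 80%, that all four figures must pass, or what follows if one does not. This stands. A reader might infer from the 82% that the plan would declare a feasible design infeasible four times in five. The documents do not support that.

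Second, the 80% may be an overall rate. Hypothesis 2 says "among recruited subjects, adherence and retention rate will be 80" per cent and attaches the figure to no arm; the by-arm definitions may only describe tabulation. This is a fair reading. It lowers the figure to 63% under independence but does not remove the problem.

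Third, independence is an assumption. Section 9 keeps participants whose settings leave the assigned range in the study, which suggests a weak link between adherence and retention. Section 3, however, lists intolerance as a reason to discontinue the intervention. The range above is the honest answer.

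Fourth, a reader might also infer that the comparison readily passes a poor design. A single arm does reach 12/15 17% of the time at a true 65% and 30% at a true 70%. If all four figures had to reach 80%, those chances would be under 1% (0.173⁴ = 0.0009 and 0.297⁴ = 0.008). The high shortfall rate and the high false-pass rate belong to different readings and cannot both be charged to the plan. Nor can 15 per arm be called unable to separate 80% from 60%: at a true 60% an arm reaches 12/15 only 9% of the time, against 65% at 80%.

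Finally, recruitment is the first feasibility outcome named, and its denominator is eligible people before randomization. It is not judged on 15 per arm.

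**Conclusion.** The concern holds in a limited form. If adherence and retention are truly 80%, an observed shortfall somewhere is more likely than not on every by-arm reading: between 58% and 82%, depending on how strongly the two are correlated. On the pooled reading it is 63% under independence and 39% if the two are identical. The figures assume 15 per arm, a true rate exactly at target, and a target read as at least 80%. They exclude recruitment, the missing-data target and the control group.

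They measure how often the report will show a number below target by chance, with nothing beside it to say so. This is a weakness in how the main question is reported and interpreted. It is not evidence that the pilot is too small for its purpose, and it calls for no change to enrolment or data collection.

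**What to change.** In section 11, Aim 2, replace the sentence on inspecting percentages with text to this effect:

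- Each feasibility rate is reported with an exact 95% interval, or with a Beta posterior (prior stated) and the posterior probability that the rate is at least 80%.
- Adherence and retention are assessed mainly on the 30 ventilated participants pooled; by-arm rates are descriptive.
- The feasibility conclusion states the range of rates the data support. It is not a met/not-met reading of the point estimate, and it does not require the whole interval to exceed 80%.

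Pooling alone would not be enough, since an observed rate below 24/30 still occurs 39% of the time per measure at a true 80%; the interval or posterior does the work. The cost is slightly more analysis and a less categorical conclusion.
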